			801	802-8XX	
			30 ± 7 days	See footnote for duration	
Physical Examination	6.1	Physical examination	X		Physical examination will include weight.
	6.1 Attachment 6	ECOG performance status	X		Refer to Attachment 6 for details.
	6.1	Vital signs	X		Includes blood pressure, pulse, and temperature.
Lab/ Diagnostic Tests	Attachment 2	Hematology	X		See Attachment 2 for details. Testing will be performed locally for patient management and centrally for analysis purposes.
	Attachment 2	Serum chemistry	X		See Attachment 2 for details. Testing will be performed locally for patient management and centrally for analysis purposes.
	Attachment 2	Coagulation profile	X		See Attachment 2 for details. Testing will be performed locally only.
	Attachment 2	Urinalysis	X		Includes a routine UA and, if clinically indicated, a microscopic analysis. If urine dipstick or routine analysis indicates proteinuria ≥2+, a 24-hour urine collection (to assess protein) must be obtained. Testing will be performed locally only.
	Attachment 2	Pregnancy test	X		Serum or urine pregnancy test. If the pregnancy test is positive, confirm with a serum or urine pregnancy test (pregnancy test results are not recorded on the eCRF). Additional pregnancy tests may be done after short-term follow-up if required by local regulation. If results are positive, the investigator is to consult with the Lilly CRP. Testing will be performed locally only.
	8.1.3.1	ECG	X		Twelve-lead ECGs are to be collected for all patients at the short-term follow-up visit. ECGs will be read locally and measurements will be electronically submitted to a central vendor.
	8.1.3.2	Echocardiogram or MUGA	X		Echocardiogram or MUGA scans are to be collected for all patients at the short-term follow-up visit.
	Attachment 4	PK sample	X		See Attachment 4 .
	Attachment 4	Immunogenicity sample	X		See Attachment 4 . In addition, if a patient experiences an IRR to olaratumab, blood samples for immunogenicity and PK analysis will be taken at the short-term follow-up after the IRR.
	8.2.3 Attachment 4	Plasma sample for exploratory biomarkers	X		Plasma sample collected at 30-day follow-up visit. See Section 8.2.3.1 for details.
	8.2.3 Attachment 4	Serum sample for exploratory biomarkers	X		Serum sample collected at 30-day follow-up visit. See Section 8.2.3.1 for details.
Efficacy Assessments	Attachment 8	Imaging Studies (CT/MRI) Tumor Assessments (according to RECIST v1.1)	X (if applicable)	X	For patients who discontinue study treatment, or complete 6 cycles of combination therapy, and have not progressed, imaging studies and tumor assessments are to be obtained every 6 weeks (±7 days) until PD, irrespective of treatment cycles, until documented progression as calculated from baseline scan. Patients who have had surgical resection will not be followed for subsequent progression by imaging studies. CT/MRI scans will be read locally and a scan will also be sent for storage at a central vendor.

Procedure Category	Protocol Section	Procedure	Study Period		Comments
			Posttreatment Discontinuation Follow-Up		
			Short-Term Follow-Up	Long-Term Follow-Up	
			Visit	801	
Duration	30 ± 7 days		See footnote for duration		
Adverse Events Collection/CTCAE Grading	8.1.2	Toxicity assessment	X	X ^a	All AEs considered at least possibly related to study treatment will be followed until resolution, stabilization, or return to baseline, or until deemed irreversible. After the 30-day short-term follow-up visit, only new and ongoing SAEs deemed related to study treatment will be collected.
Concomitant Medication Notation	7.5	Concomitant medications	X		
Patient Disposition			X	X	At the time that the patient is discontinued from study participation, information regarding the patient status will be collected.

Abbreviations: AE = adverse event; CT = computed tomography; CTCAE = Common Terminology Criteria for Adverse Events; ECG = electrocardiogram; ECOG = Eastern Cooperative Oncology Group; eCRF = electronic case report form; IRR = infusion-related reaction; MRI = magnetic resonance imaging; MUGA = multi-gated acquisition; PD = progressive disease; PK = pharmacokinetic; RECIST = Response Evaluation Criteria in Solid Tumors; SAE = serious adverse event; UA = urinalysis.

Short-term follow-up begins the day after the patient and the investigator agree that the patient will no longer continue study treatment and lasts approximately 30 days (±7 days).

The short-term follow-up visit occurs at or near the end of the short-term follow-up period (±7 days).

^a Follow up for safety: Patients who undergo surgical resection will be followed for safety for approximately 30 days (±7 days) after surgery.

Long-term follow-up begins the day after short-term follow up is completed.

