 - Platelet count $\geq 100 \times 10^9/L$.
 - Hemoglobin ≥ 9.0 g/dL. No transfusions are allowed within 2 weeks (14 days) prior to enrollment.
 - Creatinine clearance ≥ 45 mL/min (refer to [Attachment 7](#) for the Cockcroft-Gault formula).
 - Proteinuria ≤ 1000 mg in 24 hours (if routine urinalysis indicates $\geq 2+$ proteinuria).
 - Total bilirubin below upper limit of normal (ULN) (except for patients with Gilbert's Syndrome, who must have a total bilirubin < 3 mg/dL).
 - Alanine aminotransferase (ALT)/aspartate aminotransferase (AST) $\leq 3.0 \times$ ULN; if the liver has tumor involvement, AST and ALT $\leq 5.0 \times$ ULN are acceptable.
 - An adequate coagulation function as defined by International Normalized Ratio $\leq 1.5 \times$ ULN or prothrombin time $\leq 1.5 \times$ ULN, and partial thromboplastin time or activated partial thromboplastin time $\leq 1.5 \times$ ULN if not receiving anticoagulation therapy. For patients receiving anticoagulants, exceptions to these coagulation parameters are allowed if they are within the intended or expected range for their therapeutic use. Patients must have no history of active bleeding (defined as within 14 days of first dose of study drug) or pathological condition that carries a high risk of bleeding (for example, tumor involving major vessels or known esophageal varices).
- [10] Have left ventricular ejection fraction (LVEF) $\geq 50\%$ assessed within 28 days prior to enrollment.
- [11] Females of child-bearing potential must have a negative serum or urine pregnancy test within 7 days prior to enrollment.

- Exceptions: females not of child-bearing potential due to surgical sterilization (at least 6 weeks following surgical bilateral oophorectomy with or without hysterectomy or tubal ligation) confirmed by medical history or menopause.

A “postmenopausal woman” is a woman meeting either of the following criteria:

- spontaneous amenorrhea for at least 12 months, not induced by a medical condition such as anorexia nervosa and not taking medications during the amenorrhea that induced the amenorrhea (for example, oral contraceptives, hormones, gonadotropin releasing hormone, antiestrogens, selective estrogen receptor modulators, or chemotherapy)
- spontaneous amenorrhea for 6 to 12 months and a follicle-stimulating hormone level >40 mIU/mL

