7.2.3. Dose Modifications

7.2.3.1. Dose Delays, Modifications, and Discontinuations

After treatment has been initiated, in order to start the next cycle, the following criteria must be fulfilled:

- ANC $\geq 1.0 \times 10^3/\mu\text{L}$ (1000/ μL ; $\geq 1.0 \times 10^9/\text{L}$)

Note that in order to administer single-agent olaratumab on Day 8, ANC must be $\geq 750/\mu\text{L}$; $\geq 0.75 \times 10^9/\text{L}$. If the ANC is $< 750/\mu\text{L}$, the Day 8 administration of olaratumab may be delayed for a maximum of 7 days. If the ANC level has not increased to $\geq 750/\mu\text{L}$ within 7 days, then the Day 8 olaratumab dose in that cycle should be skipped and dosing resumed on Day 1 of the following cycle if criteria for dosing are met. If all dosing criteria are met, a delay or omission of the Day 8 olaratumab dose should not result in a delay of the Day 1 olaratumab dose of the following cycle.

- Platelets $\geq 100 \times 10^3/\mu\text{L}$ (100,000/ μL ; $\geq 100 \times 10^9/\text{L}$)
- Hemoglobin ≥ 8 g/dL
- Creatinine clearance ≥ 45 mL/min (refer to [Attachment 7](#) for the Cockcroft-Gault formula)
- Proteinuria ≤ 1000 mg in 24 hours (if routine urinalysis indicates $\geq 2+$ proteinuria) (to be performed every other cycle)

- Total bilirubin below ULN
- AST and ALT $\leq 3.0 \times$ ULN, or $\leq 5 \times$ ULN if the transaminase elevation is due to liver metastases
- Olaratumab-related AEs that are NCI-CTCAE Version 4.0 Grade <2 or equivalent severity to baseline

Delays:

In general, dose delays of 1 study drug (olaratumab or doxorubicin) due to toxicity guidances outlined in Sections 7.2.3.1.1 and 7.2.3.1.2 will not necessitate delays of the other study drug.

Treatment may be delayed for up to 21 days (1 equivalent cycle) to allow a patient sufficient time for recovery from study drug-related toxicity. If a patient does not recover from the toxicity within 42 days (2 equivalent cycles) from Day 1 of the previous treatment cycle, then the patient must be discontinued from study therapy.

Any procedure or sample collection whose timing is related to olaratumab dosing is to be completed according to when the olaratumab dose was actually administered, not when that dose was expected to occur. Samples whose adjusted timing would fall outside of the treatment cycle duration due to dose delay may be omitted.

Dose Modifications:

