Concomitant Medications	7.5	Concomitant Medications	X		Concomitant medications will be recorded, including any taken within 30 days prior to start of study treatment (C1D1).
Lab/ Diagnostic Tests	6.1.1 Attachment 2	Hematology	X		Screening evaluations done within 7 days prior to enrollment do not have to be repeated. Testing will be performed locally for patient management and centrally for analysis purposes.
	6.1.1 Attachment 2	Serum Chemistry	X		Screening evaluations done within 7 days prior to enrollment do not have to be repeated. Testing will be performed locally for patient management and centrally for analysis purposes.
	6.1.1 Attachment 2	Coagulation Profile	X		Screening evaluations done within 7 days prior to enrollment do not have to be repeated. Testing will be performed locally only.
	Attachment 2	Urinalysis	X		Screening evaluations done within 7 days prior to enrollment do not have to be repeated. Includes a routine UA, and if clinically indicated a microscopic analysis. If routine analysis indicates > 2+ proteinuria, then a 24-hour urine must be collected and must demonstrate ≤ 1000 mg of protein in 24 hours. Testing will be performed locally only.

		Study Period	Baseline		
		Cycle	BL		
		Visit	0		
		Duration	Up to 14 days (except where noted)		
		Relative Day from Enrollment	≤14	≤7	
Procedure Category	Protocol Sections	Procedure			Comments
Lab/ Diagnostic Tests	6.1.1 Attachment 2	Pregnancy Test		X	Serum β-HCG or urine pregnancy test (women of child-bearing potential only) within 7 days prior to enrollment. If the pregnancy test performed for inclusion purposes is positive, confirm by repeating a serum or urine pregnancy test. The results of this test will not be collected on the eCRF. Testing will be performed locally only.
	6.1.1 Attachment 2	FSH		X	Performed only at screening in menopausal women that have experienced spontaneous amenorrhea for 6 to 12 months. To be done for women only when needed to confirm postmenopausal status. Testing will be performed locally only.
	8.2.3	Tumor Tissue Biopsy		X (within 28 days of enrollment)	When submitting a tissue biopsy, sites should examine samples to determine adequacy of tumor tissue using their local laboratory procedures prior to first dose of olaratumab monotherapy. If additional tumor biopsies are collected as part of clinical care, they should be submitted, along with local pathology reports for further analysis (refer to Section 8.2.3 for details).

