	6.1	Vital Signs	X	X	X	X	Vital signs include blood pressure, pulse, and temperature. During the Observation Period (initial 2 cycles of olaratumab therapy), collect vital signs 3 times: 
 • within 15 minutes (+5 minutes) prior to olaratumab infusion • within 1 hour (+5 minutes) after completion of the olaratumab infusion • within 1 hour (+5 minutes) after completion of the doxorubicin infusion. Thereafter (Cycles 3+), obtain vital signs 2 times: within 15 minutes (+5 minutes) prior to olaratumab infusion within 1 hour (+5 minutes) after completion of the doxorubicin infusion.		
Lab/ Diagnostic Tests	Attachment 2	Hematology	X	X	X	X	Laboratory assessments may be done within 7 days prior to D1 and D8 of each cycle. See Attachment 2 for details. Testing will be performed locally for patient management and centrally for analysis purposes.		
	Attachment 2	Serum Chemistry	X		X		Laboratory assessments may be done within 7 days prior to D1 of each cycle. See Attachment 2 for details. Testing will be performed locally for patient management and centrally for analysis purposes.		
	Attachment 2	Coagulation Profile	X		X		Perform on D1 every other cycle or as clinically indicated. See Attachment 2 for details. Testing will be performed locally only.		
	Attachment 2	Urinalysis	X		X		Laboratory assessments may be done within 7 days prior to D1 of every other cycle or as clinically indicated. Includes a routine UA, and, if clinically indicated, a microscopic analysis. If routine analysis indicates >2+ proteinuria, then a 24-hour urine must be collected and must demonstrate ≤1000 mg of protein in 24 hours. Testing will be performed locally only.		
	Attachment 2	Pregnancy Test	X		X		Serum β-HCG or urine pregnancy test on D1 of every cycle or per local practice (whichever is of shorter duration). If a pregnancy test performed on D1 of the cycle is positive, confirm with a serum or urine pregnancy test (pregnancy test results are not recorded on the eCRF). If results are positive, the investigator is to consult with the Lilly CRP. Testing will be performed locally only.		
	8.2.2 Attachment 4	PK Samples	See Attachment 4 for specific time points					Whole blood samples collected for olaratumab serum PK measurements.	

Procedure Category	Protocol Section	Procedure	Study Period				Treatment Period				Comments

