Attachment 2. Protocol JGDM Clinical Laboratory Tests

All laboratory screening evaluations are to be performed within 14 days prior to enrollment, unless otherwise specified. Eligibility for inclusion in this clinical trial will be based on local clinical laboratory results (not transcribed onto electronic case report forms); duplicate samples will be submitted to the central laboratory. Treatment decisions may be based upon results of tests performed locally. Discrepancies between local and central laboratory that may have an impact on eligibility or treatment decisions will not be considered protocol deviations. On-study clinical laboratory tests assayed for patient safety (such as hematology, serum chemistry, coagulation, and pregnancy tests) are to be collected prior to study treatment.

Clinical Laboratory Tests**Hematology^{a,b}**

Hemoglobin
 Hematocrit
 Erythrocyte count (RBC)
 Mean cell volume
 Mean cell hemoglobin concentration
 Leukocytes (WBC)
 Neutrophils
 Lymphocytes
 Monocytes
 Eosinophils
 Basophils
 Platelets

Coagulation Test^a

Prothrombin time (PT)
 Partial Thromboplastin Time (PTT)
 International normalized ratio (INR)

Urinalysis^{a,c}

Specific gravity
 pH
 Protein
 Glucose
 Ketones
 Blood

Urine leukocyte esterase

Other^d

Immunogenicity samples
 PK samples
 Biomarker samples

Clinical Chemistry^{a,b}**Serum Concentrations of the following:**

Sodium
 Potassium
 Total bilirubin
 Alkaline phosphatase
 Alanine aminotransferase (ALT)
 Aspartate aminotransferase (AST)
 Blood urea nitrogen (BUN)
 Creatinine
 Uric acid
 Calcium
 Glucose, random
 Albumin
 Total protein
 Chloride
 Thyroid-stimulating hormone
 Direct bilirubin

Pregnancy test^{a,c}**Follicle-stimulating hormone (FSH)^{a,f}**

Abbreviations: CRP = clinical research physician; D = Day; PK = pharmacokinetics; RBC = red blood cells; WBC = white blood cells

- a Assayed by local or investigator-designated laboratory.
- b Duplicate samples will also be assayed by a sponsor-designated laboratory.
- c If urinary protein is $\geq 2+$ at evaluations, a 24-hour urine collection (to assess protein) must be collected and must be ≤ 1000 mg of protein in 24 hours (up to 3 business days is allowed if the weekend).
- d Assayed by a sponsor-designated (central) laboratory.

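### The baseline and on-treatment urinalysis rows of Attachment 1 trigger a 24-hour urine protein collection only above 2+, while the eligibility, next-cycle, laboratory and follow-up text triggers it at 2+ or more

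*Protocol*

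**What the plan says.** The current protocol states the trigger for a 24-hour urine protein collection in six places.

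Two use a reading strictly above 2+, with the sign standing directly before "2+ proteinuria, then a 24-hour urine must be collected":

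- Attachment 1, baseline schedule, urinalysis row: "If routine analysis indicates > 2+ proteinuria, then a 24-hour urine must be collected and must demonstrate" a total of no more than 1000 mg.
- Attachment 1, on-study-treatment schedule, urinalysis row: "If routine analysis indicates >2+ proteinuria, then a 24-hour urine must be collected and must demonstrate" the same limit.

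Four use 2+ or more:

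- Section 6.1.1, inclusion criterion 9: protein of at most 1000 "mg in 24 hours (if routine urinalysis indicates" 2+ or more.
- Section 7.2.3.1, criteria for starting the next cycle: the same limit and the same trigger, ending "proteinuria) (to be performed every other cycle".
- Attachment 2, footnote c: a urinary protein of 2+ or more "at evaluations, a 24-hour urine collection (to assess protein) must be collected and must be" no more than 1000 mg.
- Attachment 1, post-treatment follow-up schedule, urinalysis row: at 2+ or more, "a 24-hour urine collection (to assess protein) must be obtained". No limit on the result is given in this row.

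**The concern.** The threshold is operative. In Section 6.1.1 it decides whether a further result is needed to show that a patient is eligible. In Section 7.2.3.1 it does the same for starting another cycle. Attachment 1 tells sites to carry out procedures as its tables indicate, so the urinalysis row is the natural place for a coordinator to look.

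A patient who reads exactly 2+ at screening and is enrolled on that row alone would have no 24-hour value on file to show that criterion 9 was met. Section 6.1 allows no waivers of the enrolment criteria. Section 6.3.1 requires discussion with the sponsor's physician, and documented approval to continue, for a patient found not to have met them. SAP Section 5.6 names unmet entry criteria as an example of an important protocol deviation. A site could therefore meet a deviation query for having followed the table. On treatment, two patients with the same reading could be monitored differently according to which section their site consulted.

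**Working it through.** No figure in the plan depends on this threshold, so there is nothing to recalculate. The check sets the six statements side by side. It assumes the usual ordered scale for a routine urinalysis reading (negative or trace, 1+, 2+, 3+ and above), which the protocol uses without defining.

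**Step 1. Compare the two rules at each reading.**

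| Reading | Baseline and on-treatment rows (above 2+) | Criterion 9, Section 7.2.3.1, Attachment 2 footnote c, follow-up row (2+ or more) |
|---|---|---|
| Negative, trace or 1+ | not triggered | not triggered |
| 2+ | not triggered | required |
| 3+ or above | required | required |

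The rules differ at one reading only, exactly 2+.

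**Step 2. Locate the conflict by visit.**

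- Screening: the baseline row disagrees with criterion 9 and with Attachment 2 footnote c.
- On treatment: the on-treatment row disagrees with Section 7.2.3.1 and with Attachment 2 footnote c.
- Follow-up: the follow-up row agrees with Attachment 2 footnote c, so there is no conflict at that visit. It does mean that Attachment 1 uses both rules within itself.

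**Step 3. Follow the cross-references.** Both strict rows cite Attachment 2, and only Attachment 2, as their protocol section. Each therefore disagrees with the section it cites. In the baseline table the hematology, chemistry and coagulation rows cite Section 6.1.1 as well. The urinalysis row does not, so it never sends the reader to criterion 9.

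**Step 4. Count the scheduled decision points per patient.** There is one at screening. On treatment, urinalysis is due every other cycle. The protocol does not say which cycles, so take either 1, 3, 5, 7 or 2, 4, 6. The next-cycle criteria apply only once treatment has begun, that is, to Cycles 2 to 7. Either pattern puts three checks in that range (3, 5, 7 or 2, 4, 6). A patient who receives all seven cycles thus has 1 + 3 = 4 scheduled points at which the two rules could give different answers, and at each only if the reading is exactly 2+. Clinically indicated repeats would add to this.

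**Step 5. Number of patients.** The documents give no frequency of 2+ readings, so no count can be derived.

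**The case against.** The strongest reply is that a careful site can comply with everything. The schedule rows say when a collection must be done, and they do not forbid one at 2+. A site that collected at 2+ would satisfy all six statements. The criteria in Sections 6.1.1 and 7.2.3.1 are mandatory in their own right, the baseline schedule has a separate eligibility row pointing to Section 6.1, and both strict rows cite Attachment 2, where the other trigger stands.

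Much of this stands, and it limits the point. A reader might infer that sites receive opposite instructions. The documents do not support that: the conflict is between required and not triggered. A reader might also infer that the visit schedule as a whole uses the stricter sign. Only two of the three Attachment 1 tables do. Nor do the documents show that deviations will occur. That needs both a reading of exactly 2+ and a site that works from the row alone.

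The reply does not remove the contradiction. It relies on the reader finding and preferring other sections over the table that lists the procedure, and the baseline urinalysis row omits the reference to Section 6.1.1 that other laboratory rows carry.

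Two smaller objections:

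- Attachment 2 says that differences between local and central laboratory results are not deviations. Urinalysis is tested locally only, so this allowance does not help.
- A stroke lost in converting the PDF to text could turn an or-more sign into a strict one. This cannot be fully excluded but is unlikely. The strict sign appears in two separate rows, both of which keep the at-most sign before 1000 mg, and the follow-up row keeps its or-more sign.

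**Conclusion.** The protocol contradicts itself on the trigger, and the text is wrong as written. The contradiction is minor. It is confined to readings of exactly 2+ at screening and on treatment. Its consequence is operational: a site working from the two rows could enrol or re-treat a patient without the value needed to verify the criterion, with possible eligibility deviations and uneven safety monitoring. It does not touch the sample size or the primary biomarker analysis.

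A reader might go further and conclude that patients above 1000 mg in 24 hours would be enrolled. The documents do not show this. What would be missing is the evidence either way.

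The conclusion rests on the ordered reading scale and on the signs being as printed. It does not rely on the amendment summary, and it takes no view on which trigger is right.

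**What to change.** Confirm the sign in the two Attachment 1 rows against the protocol's source file. If it is as printed, reconcile the baseline and on-treatment urinalysis rows with inclusion criterion 9, Section 7.2.3.1, Attachment 2 footnote c and the follow-up row, so that all six state one trigger. Which trigger that is remains the sponsor's decision.

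The cost is one symbol in two table rows, or the matching change in the other four places, and it can be carried in the next amendment. No analysis, sample size or SAP text needs to change.
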